We hypothesize that the convenience of the STAT RT workflow will result in high patient satisfaction. The FACIT-TS-BTCSQ survey has been shown to be an effective tool in measuring the satisfaction in patients being treated for metastatic bone disease (59). Therefore, we have modified this tool to suit our patient population, and we will use this survey to measure patient satisfaction at each assessment.

Toxicity will be assessed by CTCAE Version 4.0 and RTOG Late Radiation Morbidity Scoring Criteria. These are common criteria used to assess the toxicity associated with radiation therapy. The CTCAE will assess acute toxicity, and the RTOG Late Radiation Morbidity Scoring Criteria will assess late toxicity, which is defined as toxicity that occurs 3 months or more after treatment.

**Secondary Specific Aim:** Optimize the integration of commercially available and in-development software to develop the Scan-Plan-Treat STAT RT workflow.

As described in the background, this optimization will require:

- 1) rapid co-registration of diagnostic images onto MVCT simulation images for accurate contouring and treatment planning
- 2) real-time patient-specific quality assurance using CT detectors during treatment delivery
- 3) real-time patient motion tracking to ensure accurate patient setup during MVCT simulation and treatment delivery.

To implement rapid co-registration of diagnostic images onto MVCT simulation images into the workflow, we must first confirm that this image and contour-transferring method is just as accurate as the conventional method. Again, the experimental method requires rigid and deformable co-registration of

pre-contoured diagnostic image sets to MVCT simulation scans; and in the conventional method, pre-contoured diagnostic image sets are co-registered to kilovoltage CT (kVCT) simulation images, and then kVCT simulation images are co-registered to the MVCT scan. **See Figure 4.** Contours generated from these two different registration flows will be quantitatively compared as described in detail in Section 7.1.

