Earlier we described the advantages of using the CT detector on the TomoTherapy unit with dose verification software to provide near real time 3D dose verification. We must confirm that the use of the CT detector and dose verification software yields equivalent results to conventional phantom-based quality assurance. Thus, exit radiation dose measurements and back-projected dose recalculation verification software will be compared to standard pretreatment phantom quality assurance measurements. If we prove the doses calculated by both methods to be equivalent, we could rely on only the CT detector and dose verification software for quality assurance in the future, which would further streamline the workflow.

As described in the background and preliminary studies, our in-house infrared tracking system has been developed to monitor patient positioning during simulation and treatment delivery. This infrared tracking system will be validated by 10 healthy volunteers and then used to monitor patient motion during treatments at the Emily Couric Cancer Center. The effectiveness of the infrared tracking system will be determined by comparing its position calculations with the position changes as determined by the position of the treatment set up lasers with respect to the patient's set up skin marks before and after treatment. Patient tracking is an additional experimental quality assurance process that in no way affects the patient's treatment and will not be implemented at Culpeper Regional Hospital at this time.

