**a) Optimization of Novel Image Co-registration Workflow**

The standard two step image co-registration process of contoured diagnostic images to kVCT simulation scans and then kVCT simulation scans to MVCT image guidance scans will be used to treat all patients. We will then experimentally co-register the contoured diagnostic images directly to the MVCT scan, and the PTV and OAR contours generated onto the MVCT scan by both methods will then be compared.

To evaluate the conventional and the experimental image registration flows, the two registration flows will be compared in the following manner:

- Gross tumor volumes (GTVs) will be generated from both the conventional and experimental image registration flows. The differences in volume and the distances between the two centers of the GTVs will be used to evaluate the similarity of the two GTV contours.
- Spinal cord contours will also be generated from both registration flows. The point of the spinal cord that has the shortest distance to the center of the GTV will be identified for each contour. The distance between the points from the two registration flows will be used to evaluate the similarity of the two cord contours. The volumes of the two cords will also be compared.
- Quantitative evaluation of the contours will be performed using the Dice index. Dice index is defined as the overlapping volume of two structures divided by the average volume of the two. Clearly, Dice index is 1 if the two structures are identical and 0 if they do not share any voxel. Dice index will be calculated in Velocity for contours generated on conventional and experimental image registration flows. Dice indices of 0.8 or higher are acceptable based on literature (61).

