### **7.3 Data Analyses Plans**

Treatment response as defined by International Bone Metastases Consensus Group will be determined for each patient. As described in Section 6.1.1, pain intensity as defined by the BPI and opiate use as quantified by the OMED will be used to categorize patients as having: Complete Response, Partial Response, Pain Progression, Stable Pain. At each evaluation, the patient's BPI and OMED at that visit will be compared to the pre-treatment levels. The "Worst Pain" score from the patient's BPI will be used to evaluate for treatment response. Patient response does not require a statistical analysis. The percentage of patients in each response category at each evaluation will be reported.

Patient pain will be recorded using the BPI before treatment and at designated evaluations after treatment. Pain scores before and after treatment will be compared using a Wilcoxon signed ranks test to determine if there is a statistically significant difference. Example: Pre-treatment vs. 1 week, Pre-treatment vs. 4 weeks, etc.

Analgesic use will be recorded by requiring each patient to keep a logbook of their analgesic intake. Their opiate intake for the last 72 hours will be converted to OMED at each evaluation and used in the categorization of treatment response. The difference between their OMED before and after treatment will be compared using paired two-sample t-tests.

Patients' functional status will be determined using the Karnofsky Performance Scale at each evaluation. The difference between the KPS before and after treatment will be compared using a Wilcoxon signed ranks test.

Patients' quality of life will be measured using FACT-BP and FACT-G scores at each evaluation. The difference between the FACT scores before and after treatment will be compared using a Wilcoxon signed ranks test.

Patient satisfaction will be measured using a modified version of FACT - TS – BTCSQ. No statistical analysis will be required for reporting the results. The average scores from the satisfaction survey will be reported.

To evaluate the CT detector dose calculations, the delivered radiation dose obtained using the phantom quality assurance will be compared to the exit radiation dose quality assurance calculation. The calculated dose and delivered dose for each patient will be compared using a paired two-sample t-test, and the % difference in dose will be reported.

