Contours generated from the conventional and experimental image registration flows will be compared in a variety of ways as described in Section 7.1. All comparisons of the contouring measures, including the Dice indices, will be performed using paired two-sample t-tests.

Toxicity will be recorded using CTCAE 4.0 criteria and RTOG Late Radiation Morbidity Scoring Criteria. The incidences of grade 3 or more toxicities will be reported.

The effectiveness of the infrared tracking system will be determined by comparing its position calculations with the position of the patient as determined by the position of the lasers with respect to the set up skin marks before and after treatment. The position changes calculated by each method will be compared using paired two-sample t-tests.

The average treatment planning speed of radiation treatment planning with our current clinical system will be calculated and compared the average speed of planning with newer in-development algorithms running on next generation computers with graphic processing units. These means will be compared with two-sample t-tests.

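### Section 7.3 uses paired t-tests of mean difference for technical aims that are about agreement, and Dice and the two contour distances supply no pair to test

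*Combined protocol and SAP*

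**What the plan says.** **Aims.** Section 1.5 frames two of the technical questions as agreement. On dose: "We must confirm that the use of the CT detector and dose verification software yields equivalent results to conventional phantom-based quality assurance". On registration: "we must first confirm that this image and contour-transferring method is just as accurate as the conventional method". It adds that, if the two dose methods are shown to be equivalent, exit-dose verification alone might be relied on in future. The objectives in Section 2.2 are milder and speak of optimizing and comparing.

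**Analysis.** Section 7.3 says the calculated and delivered doses "for each patient will be compared using a paired two-sample t-test, and the % difference in dose will be reported". For contours, the two workflows "will be compared in a variety of ways as described in Section 7.1", and then: "All comparisons of the contouring measures, including the Dice indices, will be performed using paired two-sample t-tests". Infrared and laser position changes in patients are also compared by paired t-tests.

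**Definitions and benchmarks.** These are in Section 7.1 under the secondary aim.

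- Item a): "Dice index is defined as the overlapping volume of two structures divided by the average volume of the two". It is computed for contours from the conventional and experimental workflows. On the cord: "The distance between the points from the two registration flows will be used to evaluate the similarity of the two cord contours". The distance between the two GTV centres is used likewise. On acceptability: "Dice indices of 0.8 or higher are acceptable based on literature".
- Item c) hopes to bring the dose software to ±3%, from a current ±5%.
- Item d) anticipates tracking accuracy of about 2-3 mm, and compares known 1-5 mm couch shifts with infrared readings in 10 volunteers.

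**The concern.** A paired t-test asks whether the average difference is zero. Agreement asks whether individual differences are small enough to ignore. The answers can diverge in both directions. Large errors of opposite sign cancel and leave a non-significant result, while a small consistent offset well inside tolerance can be significant. Section 7.3 does not say how a non-significant result will be read, and with Section 1.5's wording the natural slip is to read it as equivalence.

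For some contour measures there is a more basic problem. A paired test needs two values per case, and Dice and the two distances supply one.

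At stake are the conclusions on the secondary technical aims: whether exit-dose verification might later stand alone, and whether one-step registration is ready for the faster workflow.

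**Working it through.** **Plan's own figure.** Section 7.2 has one sample-size calculation, for the BPI change: effect size 2/3, two-sided alpha 0.05, 80% power. The Wilcoxon calculation with normal-parent efficiency 3/π gives 21, as stated. The plan makes no calculation for the technical comparisons and gives no SD of differences for them, so what follows is illustration.

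**Inputs.** n = 30 (Section 7.2), taken as one independent, normally distributed % dose difference per patient. Tolerance ±3% and current performance ±5% come from Section 7.1, item c). Assumption: each figure is a 95% range around a zero mean, so SD = 3/1.96 = 1.53% at the goal and 5/1.96 = 2.55% at current performance. A third case, mean 0.5% and SD 1%, is also assumed.

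**Formulas.** Share outside tolerance = Φ((−3 − mean)/SD) + 1 − Φ((3 − mean)/SD). Rejection probability comes from the noncentral t with 29 df, noncentrality √30 × mean/SD and critical value 2.045.

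| Mean, SD (%) | Outside ±3% | Noncentrality | t-test significant |
|---|---|---|---|
| 0, 1.53 | 5.0% | 0 | 5.0% |
| 0, 2.55 | 24.0% | 0 | 5.0% |
| 0.5, 1 | 0.64% | 5.477 × 0.5 = 2.74 | 75.4% |

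The equal 5% rates in the first two rows follow directly from assuming zero bias. With a 0.5% offset in both cases, the noncentralities are 5.477 × 0.5/1.53 = 1.79 and 5.477 × 0.5/2.55 = 1.07. Rejection is then 41% at the goal (6.2% of plans outside ±3%) and 18% at current performance (24.9% outside). For a fixed offset, tighter agreement makes a significant difference more likely.

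**Is there a pair?** Taking the measures in Section 7.1, item a) in turn:

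| Measure | Values per case | Paired test possible? |
|---|---|---|
| GTV volume, cord volume | One per workflow | Yes |
| Dice index | One, from the overlap of the two contours | No second value |
| Distance between GTV centres | One, between workflows | No second value |
| Distance between cord points | One, between workflows | No second value |

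Section 7.3 nonetheless assigns paired t-tests to every contour comparison and names Dice explicitly.

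**The case against.** The best defence is that Section 7.3 does not rest on the t-test alone. The % difference in dose is to be reported, on the same scale as the ±3% goal. The contour paragraph refers back to Section 7.1, so a reader would naturally set Dice against 0.8. These are optimization aims in a pilot. This defence stands in part: descriptive coverage exists. But no measure of spread and no criterion is attached to the % difference, and 7.1 does not say whether 0.8 applies to the mean or to each structure.

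The dose illustration can also be challenged. The plan does not say whether ±5% is a 95% range, a maximum or an average, or whether it includes a systematic offset. If optimization removed a bias, the t-test would respond. That is true, so the numbers are illustrative; the mismatch between test and aim does not depend on them.

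A pairing could be built for Dice by setting rigid against deformable registration, since the plan uses both. It is not stated, and it would not show whether the one-step route is as accurate as the conventional one.

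A reader might infer more than the documents support:

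- That the distances will be tested against zero, which would be significant almost regardless of accuracy. No section proposes that test.
- That the volunteer validation is unplanned. Section 7.1, item d) states the comparison; what is missing is a summary statistic and a pass criterion.
- That the ±5% and ±3% dose figures conflict. Item c) presents one as current performance and the other as the goal.

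**Conclusion.** The point holds. The paired t-tests in Section 7.3 cannot support the agreement claims in Section 1.5, and for Dice and the two distances the test is undefined as written. That rests on the text alone. The figures (5% rejection with either 5% or 24% of plans outside ±3%; about 75% rejection with 99.4% inside) depend on assumed means and SDs, normality, and one independent difference per patient.

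It should be fixed, but its reach is limited to secondary technical conclusions. A reader might infer a risk to trial patients. The documents do not support that: the Study Overview keeps standard quality assurance and contouring in place, and Section 7.1 says these components are not used in direct care. The primary outcome analyses are untouched.

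**What to change.** In Section 7.3, replace the t-tests as the basis for any agreement claim.

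- **Dose:** report the mean % difference, 95% limits of agreement with confidence intervals, and the proportion of plans within the ±3% goal of Section 7.1, with its interval.
- **Contours:** report mean Dice with a 95% interval against 0.8, and the proportion at or above 0.8. Give one-sample summaries with intervals for the two distances, without testing them against zero. Keep paired differences, with limits of agreement, for the volumes only.
- **Position:** report mean difference and limits of agreement in mm, read against the anticipated 2-3 mm. The same summary can serve the volunteer couch shifts.
- **Clustering:** allow for it wherever several fractions or lesions per patient enter an analysis.

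The cost is SAP wording; the measurements are already planned. The drawback is imprecision. The interval around each limit of agreement has half-width 2.045 × SD × √(1/30 + 1.96²/58) = 0.645 × SD, which is about 1.0 percentage point at SD 1.53% and 1.65 at SD 2.55%. Even 30 of 30 plans within tolerance gives an exact 95% lower bound of only 88%. Infrared data come from UVA patients only, so those intervals may be wider still.

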## 1.0 BACKGROUND AND RATIONALE

### 1.1 Study Synopsis

**Background:** Osseous metastatic disease causes significant pain, decreased functioning, and decreased quality of life. Progressive bone destruction can lead to pathologic fractures or spinal cord compression leading to orthopedic surgery, paralysis, and/or patients becoming bedridden. Opioids can alleviate pain but have neurologic and gastrointestinal side effects that further decrease quality of life. Radiation therapy can effectively reduce pain and opioid use and prevent further bone destruction, however, its use is limited because the current workflow frequently requires one week for planning and two weeks for delivery. Additionally, typical palliative radiation plans for osseous metastases lack conformality of dose to the tumor volume, and therefore, result in radiation-induced toxicity to large volumes of adjacent normal tissue. Recent software and hardware advancements provide the opportunity to revolutionize the palliative treatment of osseous metastases. We propose to investigate a novel TomoTherapy-based workflow, called STAT RT, which includes same day CT simulation, treatment planning, and quality assurance measurements coupled with highly conformal treatment delivery for patients with osseous metastases in a pilot clinical trial.

**Objective:** The overall goal of this STAT RT proposal is to develop a more rapid, convenient, and effective palliative radiation approach for patients with osseous metastases that is less toxic and less expensive than current treatment regimens. We have already optimized the conformality of TomoTherapy-based radiation doses for osseous metastases, and we have developed a STAT RT workflow that condenses standard of care simulation, planning, quality assurance, and treatment delivery into 5-6 hours. Additional optimization and integration of new radiation therapy computing processes will allow for real time simulation, planning, and delivery via a novel Scan-Plan-Treat STAT RT workflow that will ultimately require only 30 minutes. In this study we will evaluate the effectiveness of the current STAT RT workflow, and we will investigate techniques for further optimization that will be needed to create a 30 minute Scan-Plan-Treat STAT RT workflow.

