## **2.0 STUDY OBJECTIVES**

### **2.1 Primary Objectives**

Our primary objectives are to quantify outcomes of patients with osseous metastases treated via the STAT RT workflow. Specifically, we are plan to:

- 2.1.1** Estimate the response to palliative radiation as defined by International Bone Metastases Consensus Group using the BPI and OMED to categorize into Complete Response, Partial Response, Pain Progression, and Stable Pain after receiving treatment via the STAT RT workflow.
- 2.1.2** Estimate the change in the patient's quality of life and function as scored by FACT-BP and KPS after receiving treatment via the STAT RT workflow.
- 2.1.3** Estimate patient satisfaction with the STAT RT workflow using a modified FACIT-TS-BTCSQ survey.
- 2.1.4** Report the treatment-related toxicity using CTCAE Version 4 and RTOG Late Radiation Morbidity Scoring Criteria after receiving treatment via the STAT RT workflow.

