#### **4.10 Expected Adverse Events**

Depending on the site of treatment, potential / expected treatment toxicities include Grade 1 to 3 toxicity of the following symptoms, with Grade 3 occurring in no more than the following percentages of patients:

|             |     |
|-------------|-----|
| Dermatitis  | 20% |
| Nausea      | 20% |
| Fatigue     | 20% |
| Vomiting    | 20% |
| Diarrhea    | 20% |
| Mucositis   | 20% |
| Esophagitis | 20% |

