## **6.2 Toxicity and Safety**

All patients who receive treatment on this protocol will be evaluable for toxicity using the National Cancer Institute (NCI) Common Terminology Criteria for Adverse Events (CTCAE) Version 4 and the RTOG Late Radiation Morbidity Scoring Criteria at time points indicated in the Time and Events table in Section 5.1.

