**1) Primary Aim: Evaluation of Outcomes of Patients with Osseous Metastases Treated with STAT RT**

We will recruit 30 cancer patients with 1-3 painful osseous metastatic lesions (target sites) requiring opioid medication who are candidates for palliative radiation therapy. Patients will receive 2-5 fractions of 5-10 Gy (minimum BED of 25 Gy) of conformal radiation therapy delivered to the target sites via the Helical TomoTherapy system using the STAT RT workflow. Patient pain, analgesic use, function, quality of life, and satisfaction will be recorded prior to treatment, at 1 week, 4 weeks, 8 weeks, 12 weeks, 6 months, and 12 months after therapy using the following measures:

- a) The Brief Pain Inventory (BPI)
- b) Patients will keep an analgesic use logbook and have their doses converted into Oral Morphine Equivalent Doses (OMED).
- c) Treatment response will be measured by the guidelines set forth by the International Bone Metastases Consensus Group as described in Section 6.1.1.
- d) The FACT-BP and FACT-G questionnaires
- e) Karnofsky Performance Scale (KPS)
- f) Patient Satisfaction will be measured by a modified FACIT-TS-BTCSQ survey.

Radiation-induced treatment related toxicities will be captured during treatment and at the above time points and graded using the CTCAE Version 4.0 and the RTOG Late Radiation Morbidity Score Criteria.

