## **8.4 UVA Cancer Center DSMC AE Reporting Requirements**

All adverse events will be recorded on appropriate case report forms. In addition, AE Reporting will occur via the UVA Cancer Center clinical trials reporting system, C3TO (TABLE Below).

| Therapeutic Medium Risk Phase II Studies   |                         |              |              |          |                         |                      |                         |                      |           |
|---|-------------------------|--------------|--------------|----------|-------------------------|----------------------|-------------------------|----------------------|-----------|
| Reporting requirements for AEs that occur within 30 days of the last dose of protocol specified treatment |                         |              |              |          |                         |                      |                         |                      |           |
|   | Grade 1                 | Grade 2      |              | Grade 3  |                         |                      |                         | Grade 4 & 5          |           |
|   | Expected and unexpected | Expected     | Unexpected   | Expected | Without hospitalization | With hospitalization | Without hospitalization | With hospitalization | Expected  |
| Unrelated   | Not required            | Not required | Not required | C3TO     | C3TO                    | C3TO                 | C3TO                    | C3TO                 | C3TO      |
| Unlikely  |                         |              |              | 30 days  | 15 days                 | 30 days              | 15 days                 | 15 days              | 15 days   |
| Possible  | C3TO                    | C3TO         | C3TO         | C3TO     | C3TO                    | C3TO                 | C3TO                    | C3TO                 | C3TO      |
| Probable  | 30 days                 | 30 days      | 15 days      | 30 days  | 15 days                 | 15 days              | 15 days                 | 15 days              | (24-hrs)* |

|          |  |  |  |  |  |  |  |  |        |
|----------|--|--|--|--|--|--|--|--|--------|
| Definite |  |  |  |  |  |  |  |  | 7 days |
|----------|--|--|--|--|--|--|--|--|--------|

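### Section 7.3 plans a toxicity summary at Grade 3 or higher only, although primary objective 2.1.4 has no grade cut-off and all grades are collected to 12 months

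*Combined protocol and SAP*

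**What the plan says.** Toxicity is one of four primary objectives. Objective 2.1.4 is to "Report the treatment-related toxicity using CTCAE Version 4 and RTOG Late Radiation Morbidity Scoring Criteria", with no grade limit.

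Collection covers the whole scale. Under the primary aim in section 7.1, toxicities are "captured during treatment and at the above time points and graded using the CTCAE Version 4.0" and the RTOG late criteria. The Time and Events Table (5.1) schedules toxicity evaluations during treatment, at weeks 1, 4, 8 and 12, and at 6 and 12 months. Section 6.2 states: "All patients who receive treatment on this protocol will be evaluable for toxicity". Section 8.4 states: "All adverse events will be recorded on appropriate case report forms". Section 1.5 assigns CTCAE to acute effects and RTOG to late effects, the latter starting 3 months after treatment.

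On what is expected, section 4.10 says "potential / expected treatment toxicities include Grade 1 to 3 toxicity" and puts a 20% ceiling on Grade 3 for each of seven listed symptoms.

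On analysis, section 7.3 names the two scales and then says: "The incidences of grade 3 or more toxicities will be reported". No other toxicity summary is listed, and the section gives no denominator, attribution rule or interval for it.

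The synopsis (1.1) describes the overall goal as an approach "that is less toxic and less expensive than current treatment regimens".

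**The concern.** The objective and the data cover every grade; the planned analysis covers only the top of the scale. Elsewhere section 7.3 is fuller: for pain response it reports the percentage in each of the four categories, not just the extreme ones.

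What falls below the cut-off is not trivial on the protocol's own scale. In Appendix F, RTOG Grade 2 includes being unable to eat solids normally (esophagus), severe L'Hermitte's syndrome (spinal cord) and symptomatic pneumonitis with severe cough (lung). Section 1.3.7 says the primary aim is to establish both benefits and risks of the workflow. A results section that follows 7.3 literally would leave these effects out.

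**Working it through.** **Step 1. The plan's own figures.** The only computed figure in the statistical section is n = 21 for the before/after pain comparison (7.2: mean change 2, SD 3, two-sided alpha 0.05, 80% power). It reproduces: with a standardised change of 2/3 and the Wilcoxon efficiency of 3/π against the paired t-test, n = 21 gives power 0.808. It has no bearing on toxicity. The only toxicity figure is the 20% Grade 3 ceiling in 4.10.

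**Step 2. Scope, set side by side.**

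| Item | Grades covered | Source |
|---|---|---|
| Primary objective | No limit | 2.1.4 |
| Expected events | 1 to 3 | 4.10 |
| Graded assessments | Full CTCAE and RTOG scales, to 12 months | 5.1, 6.2, 7.1 |
| Planned summary | 3 and above | 7.3 |

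**Step 3. Does safety reporting fill the gap?** The C3TO table in 8.4 covers events within 30 days of the last dose and does not require Grade 1-2 events judged unrelated or unlikely. Section 8.1.1 also ends adverse event collection at 30 days. Late effects begin at 3 months, so late Grade 1-2 effects have neither a C3TO route nor a planned summary. Earlier related Grade 1-2 events do reach C3TO, but that is oversight rather than reporting of an outcome.

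**Step 4. How informative is a Grade 3+ summary in 30 patients?** N = 30 is from 7.2. The rates of 1%, 2% and 5% are assumptions; 20% is the ceiling in 4.10. The chance of no event is (1 − p)^30.

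| True Grade 3+ rate p | Expected patients, 30p | P(no event) |
|---|---|---|
| 1% (assumed) | 0.3 | 0.99^30 = 0.740 |
| 2% (assumed) | 0.6 | 0.98^30 = 0.545 |
| 5% (assumed) | 1.5 | 0.95^30 = 0.215 |
| 20% (ceiling, per symptom) | 6.0 | 0.80^30 = 0.001 |

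With 0 of 30, the exact two-sided 95% upper limit is 1 − 0.025^(1/30) = 11.6%. With 6 of 30 (20%), the exact 95% interval is 7.7% to 38.6%.

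**Step 5. What would be left out.** If a Grade 1-2 effect occurred in 12 of 30 patients (an assumed 40%), its exact 95% interval would be 22.7% to 59.4%. That is a usable estimate, but 7.3 gives it no place.

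**Step 6. Denominator for late effects.** Eligibility requires a life expectancy of only more than 12 weeks (3.1.14), and section 5.4 expects hospice losses. Suppose, as an assumption, that 15 of 30 patients are assessed at 3 months or later and 3 have a late Grade 2 effect. Then 3/30 = 10% but 3/15 = 20%. Using all treated patients would understate late rates.

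**The case against.** The strongest reply is that this is a gap in wording. Section 7.3 does not say that only Grade 3 or higher will be reported, and 2.1.4 separately commits the trial to reporting treatment-related toxicity. That is fair as far as it goes: nothing forbids lower grades. But no section promises them either, and 7.3 is where the analysis is specified. The mismatch stands.

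Second, low-grade effects are not wholly invisible. FACT-G asks about nausea, lack of energy and being bothered by side effects (Appendix B), its scores are compared before and after treatment, and the DSMC reviews all adverse events (9.2). This is true, but FACT scores are neither graded nor attributed to radiation.

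Third, low-grade events are hard to interpret here. Chemotherapy may be concurrent (3.1.11) and the Time and Events Table has no pre-treatment toxicity evaluation, so Grade 1-2 nausea or fatigue will partly reflect disease and other treatment. This stands, and is why the table should be limited to treatment-related events and show attribution.

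A reader might also infer something stronger: that Grade 1-2 is where an advantage over conventional radiotherapy would show, so the cut-off hides it. The documents do not support that. The trial is non-randomized, with no control arm, toxicity benchmark or toxicity test, so no difference can be shown at any grade. Section 4.10 allows Grade 3 up to 20% per symptom, and section 1.2.2 lists the side effects of conventional fields without grades. Lower toxicity is the overall goal of the STAT RT proposal in 1.1, not part of the primary hypothesis there, which concerns pain relief, quality of life and satisfaction.

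**Conclusion.** The point holds as one of reporting scope. Section 7.3 delivers only part of primary objective 2.1.4: treatment-related Grade 1-2 effects, including late RTOG Grade 2 effects, are collected but have no place in the planned analysis.

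Its size depends on the unknown Grade 3+ rate. If that rate is 1% to 5%, the planned summary would show no event with probability 74% down to 21%. Section 1.3.7 reports minimal acute toxicity in patients already treated, which makes low rates plausible, but gives no figures. At the 20% ceiling, about 6 of 30 patients would appear for each symptom and the summary would carry real information. It is therefore incomplete, not necessarily empty. That 7.3 is exhaustive is inferred from the absence of any other toxicity summary. No design feature, sample size or safety rule is affected.

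**What to change.** Replace the sentence in 7.3 with text to this effect:

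*For each CTCAE term and each RTOG organ with at least one event, the number and percentage of patients will be tabulated by worst grade of treatment-related toxicity, showing attribution. Acute and late toxicity will be tabulated separately, with exact 95% confidence intervals for Grade 2 or higher and for Grade 3 or higher. The denominator is all treated patients for acute toxicity. For late toxicity it is patients with at least one toxicity evaluation at 3 months or later, and the number assessed will be shown. The trial has no comparator, so whether this treatment is less toxic than current regimens is not tested.*

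The text should also say whether the week 12 visit counts as acute or late: 12 × 7 = 84 days, slightly short of three calendar months.

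The cost is a longer descriptive table from data already collected. The remaining weakness is that some low-grade events will reflect disease or concurrent chemotherapy; showing attribution reduces this but does not remove it. Sample size, alpha and power do not change.
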